**Trademark Information**

Trademarks of the GlaxoSmithKline group of companies	Trademarks not owned by the GlaxoSmithKline group of companies
NONE	KEYTRUDA LIBTAYO OPDIVO

## 12.13. Appendix 13: Protocol Amendment History

The Protocol Amendment Summary of changes Table for the current Amendment 05 is located directly before the Table of Contents (TOC).

**Amendment 04 (Sub-study 4) 14-DEC-2020**

### Overall Rationale for the Amendment:

The 208887 protocol has been amended to convert to a modular document format with separate Master Protocol (MP) and Sub-study modules. The organizational changes for Sub-study 4 are administrative and are mapped in the table below.

Section # for PA3 and Name	Section # for PA4 and Name
14.1 Schedule of Activities Tables	1.3 Schedule of Activities (SoA)
14.2 Background of Dostarlimab	2.2 Background for Dostarlimab
14.2.1 Clinical Experience with Dostarlimab	2.2.1 Clinical Experience
14.2.2 Pharmacokinetic Summary of Dostarlimab	2.2.2 Pharmacokinetic Summary
14.2.3 Safety for Dostarlimab	2.2.3 Safety
	8.3.10 Adverse Events of Special Interest
14.3.1 Rationale for the Combination	2.1 Rationale for combination of Belantamab mafodotin with Dostarlimab
14.3.2 Dose justification for Dostarlimab when in combination with Belantamab Mafodotin	4.3 Justification for Dose
14.3.3 Potential for Drug-Drug Interactions (DDIs) between Belantamab Mafodotin and Dostarlimab	2.2.3.1 Potential for Drug-Drug Interactions (DDIs) between Belantamab Mafodotin and Dostarlimab
14.3.4 Benefit/Risk	2.3 Benefit/Risk Assessment
14.4 Study Design Details	6.2 Administration of Belantamab mafodotin and Dostarlimab
14.4.1 Dostarlimab Dosing Frequency	
14.4.2 Study Intervention(s) Administered - Belantamab Mafodotin and Dostarlimab	
14.4.2.2 Treatment of Overdose	8.4 Treatment of Overdose
14.4.3 Study Intervention Product and Accountability	6.3 Preparation/Handling/Storage/Accountability – content deleted as it was identical to the 208887 MP
14.4.4 Combination Treatment Belantamab Mafodotin (GSK'916) Co-Administered with Dostarlimab (GSK'190)	4.1 Overall Design
14.4.5 Treatment Duration of Dostarlimab	6.2 Administration of Belantamab mafodotin and Dostarlimab
14.4.6 Dose modification for Belantamab Mafodotin when in combination with Dostarlimab	6.6 Dose Modification
14.4.7 Inclusion/Exclusion Criteria for Dostarlimab Sub-study	5.1 Inclusion Criteria for Participants
	5.2 Exclusion Criteria
14.4.8 Management of Pregnancy	8.3.7 Management of Pregnancy
14.5 References	10 References
14.6 Appendices	11 Guidelines for dose modification and other partner combination treatments for all substudies

Changes listed in the table below are for the Sub-study 4 protocol only. Changes for Protocol Amendment 4 that are related to the 208887 Master Protocol and specific sub-studies are tabulated at the beginning of each relevant Sub-study module.

Section # and Name	Description of Change	Brief Rationale
Changes in Assessments and SoAs		
1.3. Schedule of Activities	Clarified footnote on Single ECG at Screening (Table 3)	Clarified based on prior edits (Protocol Amendment 03)
	Extraction of information regarding BM Assessments in a separate table (current Table 6)	To clarify assessments
	Clarified FISH assessments that are to be completed at Screening (Table 6) based on availability on previous results	In line with other protocols in the program.
	Added footnote 20c for supportive care information (Table 4)	To align with belantamab mafodotin program guidelines
	Added language on biomarker assessments for PD-L1 expression (Table 6)	To clarify biomarker assessments for the Sub-study 4 combination
	Clarified language on definition of resolution of ophthalmic findings (to baseline instead of Grade 1)	To align with GSK belantamab mafodotin program language
8.8 Biomarkers	Addition of language for prospective evaluation of PD-L1	To clarify assessments for the Sub-study 4 combination
Editing, format, style changes		
Throughout	Correction of typos and technical document aspects	Minor changes; no impact on content

1. INTRODUCTION

The purpose of this SAP is to describe the planned analyses to be included in the CSR for Study 200887 sub-study 4. For more details about the statistical analysis and plan for the overall study refer to the Master SAP. This sub-study was terminated early during the Dose Escalation (DE) phase; therefore, this sub-study SAP will focus only on the DE phase.

1.2. Objectives, Estimands and Endpoints

The primary and secondary objectives, along with the corresponding endpoints for DE phase are listed in [Table 2](#)

Table 2 Dose Exploration (DE)

Objectives	Endpoints
Primary	
To determine the safety and tolerability of belantamab mafodotin in combination with Dostarlimab and to establish the recommended Phase 2 dose for the combination treatment to explore in the CE Phase in participants with RRMM.	
 Percentage (number) of participants with dose limiting toxicities (DLTs) Percent of subjects with AEs, changes in clinical signs and laboratory parameters

Objectives	Endpoints
Key Secondary	
To evaluate the clinical measures of efficacy of belantamab mafodotin and Dostarlimab in participants with RRMM	
 • Clinical activity measured as Overall Response Rate (ORR) according to the International Myeloma Working Group (IMWG) Response Criteria (Kumar , et al., 2016)
Secondary	
To further evaluate the clinical measures of efficacy of belantamab mafodotin and Dostarlimab in participants with RRMM	
Rates of:
 
 • Partial Response (PR); • Very Good Partial Response (VGPR); • Complete Response (CR); • Stringent Complete Response (sCR)
To describe the exposure of belantamab mafodotin when administered in combination with Dostarlimab in participants with RRMM	
 • Belantamab mafodotin observed concentration
To describe the exposure of Dostarlimab when administered in combination with belantamab mafodotin.	
 • Combination of belantamab mafodotin with Dostarlimab treatment's observed concentration.
To assess anti-drug antibodies (ADAs) against belantamab mafodotin and against combination treatments (biologics) that are administered by IV infusion.	
 • Incidence and titers of ADAs against belantamab mafodotin and its combination with Dostarlimab, when measured.
To further determine the safety and tolerability of belantamab mafodotin in combination with Dostarlimab	
 • AEs of special interest for belantamab mafodotin • AEs of special interest for belantamab mafodotin in combination with Dostarlimab • Ocular findings on ophthalmic exam

1.3. Study Design

Overview of Study Design and Key Features				
Please refer to the 208887 Master SAP for overall Study Design for the study.				
Design Features	
 Refer to the 208887 Master SAP for the key design features for the study 			
Study intervention	
 The Starting Dose (SD) for belantamab mafodotin in study 208887 will be 1.9 mg/kg Q3W in combination with other anti-cancer treatments but may vary by sub-study. Dostarlimab is to be given at least one hour following completion of belantamab mafodotin infusion. 			
Dose Level	Belantamab Mafodotin mg/kg IV Q 3 weeks	Dostarlimab mg IV Q 3 weeks	Dostarlimab mg IV Q 6 weeks	
1	1.9 mg/kg	500 mg, cycles 1 – 4	1000 mg, cycle 5 and every odd cycle thereafter	
2	2.5 mg/kg	500 mg, cycles 1 – 4	1000 mg, cycle 5 and every odd cycle thereafter	
	
 Dostarlimab will be administered as a 30-minute IV infusion at the prescribed flat dosing 			
Time & Events	
 Refer to Section 1.3: Schedule of Activities (SoA) in Sub-study 4 modular protocol 			
Treatment Assignment	
 In DE phase, treatments will be assigned to participants with predefined algorithm. 			
Interim Analysis	
 The Interim Analysis (IA) planned in the DE will not be carried out. 			
Blinding	
 This is an open label study. In DE phase, participants will be assigned to available treatment slots by a predetermined algorithmic approach. 			

2. STATISTICAL HYPOTHESES

In the DE Phase, the primary objective is to determine the safety and tolerability of belantamab mafodotin and dostarlimab. No formal statistical hypothesis will be tested.

2.1. Multiplicity Adjustment

Analyses of any efficacy endpoints will not be subject to any multiplicity adjustment since each sub-study is analysed separately.

3. ANALYSIS SETS

Refer to the 208887 Master SAP Section 3 for the complete list of analysis sets for this study.

4. STATISTICAL ANALYSES

4.1. General Considerations

4.1.1. Final Analysis

GSK decided that no further enrolment will take place on this sub-study. As a result, all analyses corresponding to the CE phase, as well as the exploratory endpoints for both the DE and CE phase will not be performed.

The final analyses will be performed after all required database cleaning activities have been completed on available DE data and final database release (DBR) and database freeze (DBF) has been declared by Data Management.

4.1.2. Study Treatment & Sub-group Display Descriptors

Phase	Description
DE	1.9mg/kg GSK916 + 500mg Q3W DOSTAR
	1.9mg/kg GSK916 + 1000mg Q6W DOSTAR ¹
	2.5mg/kg GSK916 + 500mg Q3W DOSTAR ¹
	2.5mg/kg GSK916 + 1000mg Q6W DOSTAR ¹

¹ Note that this dose level was not used due to early termination

4.1.3. Baseline Definition

Refer to the Master SAP Section 4.1.4 for details on baseline definitions.

4.2. Primary Endpoint(s) Analyses

Primary analysis for the DE phase involves summaries of the number and percentages of participants with DLTs and AEs. Both DLTs and AEs will be summarised and listed. All analyses for the DE phase will be based on the Safety population, unless otherwise specified.

4.3. Secondary Endpoint(s) Analyses

Due to this sub-study being terminated early during the DE phase, there will be no primary efficacy analysis for the CE phase as these data were not collected.

4.3.1. Key Secondary Endpoint

For the definition of the key secondary endpoint, ORR, along with the derivation of confirmed response table please refer to Section 4.2.2.1 of the MSAP.

A summary of investigator assessed best response with confirmation will be produced, using the Safety population.

4.3.2. Secondary Endpoints

Best Overall Response rates (i.e Partial Response (PR) rate, Very Good Partial Response (VGPR) rate, Complete Response (CR) rate and Stringent Complete Response (sCR) rate) will be reported within the summary table described in Section 4.3.1.

The derivation of confirmed response table in Section 4.2.2.1 of the MSAP, will be used confirm the secondary endpoints.

BOR and corresponding response rates will be summarized using descriptive statistics and listed. The corresponding 95% exact CI will also be provided. Participants with unknown or missing responses will be treated as non-responders, i.e., these participants will be included in the denominator when calculating percentages of response.

Other secondary endpoints, PK, ADAs, and AESIs can be found in the sections below.

4.4. Exploratory Endpoint Analyses

Analysis of exploratory endpoints will not be performed for neither the DE nor CE phase, due to the early termination of the sub-study.

4.5. Safety Analyses

The safety analyses will be based on the Safety Analysis Set, unless otherwise specified. Unless otherwise specified, on-treatment AE's will be reported.

4.5.1. Extent of Exposure

Refer to the Master SAP Section 4.5.1 for details on the extent of exposure for this study. The cycle length term Q3W is equivalent to a cycle length in days of 21 days, to be used in calculations for treatment exposure.

Extent of exposure to belantamab mafodotin monotherapy and combination therapy will be summarized.

A 'by participant' listing of data on exposure to all study treatments will be produced.

Dose reductions will be summarised by number of reduction and reasons for reductions. Dose delays/interruptions will be summarised by number of delays, and delay duration (days). All the dose reductions and dose delays/interruptions will be listed.

4.5.2. Adverse Events

Summaries of all AEs, all drug-related AEs, common non-SAEs, SAEs, and AEs leading to permanent discontinuation of study treatment will be reported by system organ class, preferred term and maximum grade.

Listings of all AEs, fatal SAEs, non-fatal SAEs, reasons for considering as a SAE and AEs leading to permanent discontinuation will be reported.

Dose limiting toxicities (DLTs) will also be summarised and listed.

4.5.2.1. Adverse Events of Special Interest

Refer to the Master SAP Section 4.5.2.1 for details on AESI. The list of terms and reporting requirements for GSK AESI, and the known list of AESIs for GSK'916 can be found in Section 8.3.10 of the Sub-Study 4 protocol.

A summary of corneal events by grade will be provided using the GSK scale for all those participants who has an event under protocol amendment 1; using CTCAE scale for all those participants who had an event under protocol amendment 2 or 3, and using KVA scale for those patients who had an event under protocol amendment 4. Corresponding listings for ocular events will also be reported, along with a listing of visual acuity by grade.

The grading scales for the GSK and KVA scale for corneal events can be found in Table 6 and Table 7 in the MSAP respectively. For guidance of grading based on changes in visual acuity refer to Table 8 in the MSAP.

4.5.2.2. Immune-related Adverse Events (irAEs)

irAEs will be graded by the investigator according to the National Cancer Institute-Common Terminology Criteria for Adverse Events (NCI-CTCAE), Version 5. irAE will be coded using the standard Medical Dictionary for Regulatory Affairs (MedDRA dictionary, version 25.0) and grouped by SOC.

A summary of all immune-related adverse events by system organ class, preferred term and maximum grade, and a listing containing all immune-related adverse events will be produced.

4.5.2.3. COVID-19 Assessment and COVID-19 AEs

A Standardised MedDRA Query (SMQ) will be used to identify all COVID-19 AEs.

The impact of COVID-19 on DLTs during the DE phase of any sub-study will be monitored during the study conduct through review of protocol deviations. DLTs will be reported according to the DLT evaluable population in Section 3 of the MSAP.

The incidence of AEs and SAEs (Fatal and Non-Fatal) of COVID-19, COVID-19 AEs leading to study drug discontinuation, and COVID-19 AEs leading to study withdrawal,

and COVID-19 AEs by severity, will be obtained from standard AE and SAE summaries and listings.

4.5.2.4. Deaths and Serious Adverse Events

All deaths will be summarised based on the number and percentage of participants. This summary will classify participants by time of death relative to the last dose of medication (>30 days or ≤30 days) and primary cause of death (disease under study, SAE related to study treatment, or other). A supportive listing will be generated to provide participant-specific details on participants who died.

All SAEs associated with belantamab mafodotin monotherapy will be tabulated based on the number and percentage of participants who experienced the event. Separate summaries will also be provided for study combination treatment-related SAEs. The summary tables will be displayed in descending order of total incidence by SOC and PT.

A study treatment-related SAE (or serious irAE) is defined as an SAE (or serious irAE) for which the investigator classifies the relationship to study treatment as “Yes”. A worst-case scenario approach will be taken to handle missing data, i.e. the summary table will include events with the relationship to study treatment as ‘Yes’ or missing.

4.5.2.5. Adverse Events Leading to Discontinuation of Study Treatments and Other Significant Adverse Events.

The following categories of AEs will be summarized separately by individual treatment component and combination (belantamab mafodotin monotherapy and GSK'190 (dostarlimab) + belantamab mafodotin) as collected in descending order of total incidence by SOC and PT and separate supportive listings will be generated with participant level details for those participants:

- AEs Leading to Permanent Discontinuation of Study Treatment
- AEs Leading to Dose Interruptions or Delays
- AEs Leadings to Dose Reductions
- All Treatment-related Serious Adverse Events

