5. SAMPLE SIZE DETERMINATION

In the DE phase, approximately up to 10 participants were to be assigned to the combination dose level. However, the study was terminated early due to lack of efficacy; therefore only 4 participants were enrolled onto dose 1.

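### Does the label belantamab mafodotin monotherapy in SAP 4.5.1, 4.5.2.4 and 4.5.2.5 undermine the safety tables of a sub-study in which every participant was assigned the combination?

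*SAP*

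**What the plan says.** The SAP uses the monotherapy label in three places:

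- Section 4.5.1: "Extent of exposure to belantamab mafodotin monotherapy and combination therapy will be summarized".
- Section 4.5.2.4: "All SAEs associated with belantamab mafodotin monotherapy will be tabulated based on the number and percentage of participants who experienced the event". Separate summaries follow for related serious events of the combination.
- Section 4.5.2.5: "The following categories of AEs will be summarized separately by individual treatment component and combination (belantamab mafodotin monotherapy and", and the bracket then continues with dostarlimab plus belantamab mafodotin. The split is qualified as depending on what was collected.

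Relatedness is defined once in 4.5.2.4, as an event "for which the investigator classifies the relationship to study treatment as" yes, with missing answers counted as yes. The definition does not distinguish between the two drugs.

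The rest of the SAP describes a combination only. The Introduction says "this sub-study SAP will focus only on the DE phase". Section 4.1.2 lists four display groups, each with both drugs. The only one not footnoted as unused is "1.9mg/kg GSK916 + 500mg Q3W DOSTAR". Section 5 says "therefore only 4 participants were enrolled onto dose 1". Protocol Section 6 defines study intervention as belantamab mafodotin given together with its partner.

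**The concern.** A table headed monotherapy should hold people who received one drug, and this sub-study has no such group. Read literally, the column has no denominator. Read as events attributed to belantamab, it holds people assigned both drugs under a heading that misdescribes them, and a later reader might reuse the table as single-agent safety data. With a single relatedness question, the SAP text available also gives no rule for choosing which serious events belong to the supposed monotherapy.

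The bracket in 4.5.2.5 adds a second oddity. It follows a promise to report each component, yet dostarlimab appears only inside the combination. The primary objective is the safety of this pairing. A programmer who took the bracket as exhaustive would produce no summary of actions taken on dostarlimab alone, such as the skipped dose that Protocol Section 6.2 allows after an infusion reaction to belantamab.

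**Working it through.** The plan states no derived figure on this point, so the check is a count and a comparison of sections.

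**1. How often the label occurs, and whether any group matches it.**
- Occurrences: 1 (4.5.1) + 1 (4.5.2.4) + 1 (4.5.2.5) = 3.
- Display groups without dostarlimab (4.1.2): 0 of 4. Three of the four are footnoted as not used, so 4 − 3 = 1 group was used, and it is a combination.
- Participants assigned to monotherapy (SAP 5, with the dose table in SAP 1.3): 0 of 4.

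**2. What the label could mean.**
- A treatment group: N = 0, so percentages are undefined. No analyst would build this table.
- The belantamab component within the combination: N = 4, if all enrolled participants are in the Safety population. The component wording in 4.5.2.5 points this way.
- Cycles given without dostarlimab: anywhere from 0 to 4 participants. Protocol Section 6.2 allows a skipped dostarlimab dose. From cycle 5 the schedule in SAP 1.3 also gives dostarlimab on odd cycles only, but 4.1.2 marks the 1000 mg group at 1.9 mg/kg as not used. Neither document calls such cycles monotherapy.

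The second reading fits all three sentences best.

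**3. What the bracket leaves out.** Components with their own entry: 1 of 2. The governing words of the sentence still call for each component as collected, so they cover dostarlimab wherever the case report form recorded action by drug. How often the two drugs' actions would differ is limited:
- Protocol Section 6.6 and the notes to Table 4 tie dostarlimab to belantamab. When belantamab is held or stopped for toxicity, so is dostarlimab.
- Section 6.6 allows no dose reduction of dostarlimab, so that category has no dostarlimab content.
- The skipped dose in Section 6.2 clearly concerns dostarlimab alone. The discontinuation rules for encephalitis (Section 6.6, Table 11) and for severe infusion reactions to dostarlimab (Table 8) do not say whether belantamab goes on.

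**4. What is reported without the label.** Each of the four categories in 4.5.2.5 has an unsplit counterpart or a listing:
- Permanent discontinuation: summary and listing in 4.5.2, and the discontinuation listing in 6.1.1 with last dose date, reason and relatedness.
- Interruptions and delays: number and duration summarised in 4.5.1, and all of them listed.
- Reductions: number and reasons summarised in 4.5.1, and all of them listed.
- Treatment-related serious events: the combination summary in 4.5.2.4, with all serious events summarised and listed in 4.5.2.

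In addition, 4.5.2.2 gives a summary and listing of immune-related events, 4.5.2.5 promises supportive listings of its own, and 4.5.1 says that a by-participant "listing of data on exposure to all study treatments will be produced". Exposure to either drug can be read from that listing for each of the 4 participants.

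**The case for a change.** The strongest argument for a change is that these sections specify outputs for the clinical study report and that correct tables elsewhere do not repair a wrong heading. Correction would be cheap, since only wording and table shells are involved. The partner drug, whose addition is what the sub-study examines, is the component left without its own entry. The coupling rule also runs one way: holding belantamab for toxicity holds dostarlimab, but the protocol supplied does not state the reverse. A dostarlimab-only action is therefore possible and would be the more informative one to show.

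Part of this stands. The label is wrong as English, and the bracket does not match its own sentence. The rest weakens on inspection. The display descriptors in 4.1.2 name both drugs, so tables built on them would tell the reader that these people received the combination. The platform title in the Protocol Synopsis covers belantamab both as monotherapy and in combination, which makes shared template wording a likely source. Any dostarlimab-only action would show in the listings, where data on 4 people can be read line by line, and no such action is documented for these participants. Splitting relatedness by drug may be impossible in any case, because the SAP defines a single answer for study treatment.

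**Conclusion.** This is a clerical slip, and correcting it would bring no analytical gain. Three phrases carry a label that fits 0 of 4 display groups and 0 of 4 participants, and one bracket gives 1 of 2 components its own entry. No event is lost and no estimate moves. The dose exploration analysis is descriptive, and SAP Section 2 rules out a formal hypothesis test. An analyst would read the label as the belantamab component and follow the component wording in 4.5.2.5 for dostarlimab where the data allow.

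This rests on three assumptions. First, the label means the component, which is an inference from the surrounding text. Second, all 4 enrolled participants belong to the Safety population; the SAP gives enrolment and leaves the definition of the analysis sets to the Master SAP. Third, nothing in the Master SAP or the document of planned displays sets up a real monotherapy column. Neither was available. The SAP sends the details of exposure to the first and of planned displays to the second, so they may already define the term or include dostarlimab separately. If the term survives into the report, a footnote to the table stating that all participants were assigned both drugs would be enough.
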